5.5 RANDOMISATION

5.5.1 Randomisation Procedures

A web-based computer-generated randomisation process will be used to ensure allocation concealment and reduce bias. The randomisation system will be provided by ECTU and patients will be randomised using their unique health identifier to prevent inadvertent duplicate randomisation. International sites will use their own randomisation system which will be described in their country specific protocol. Randomisation will be by permuted-block with a level of stratification for

each of the following groups of patients: (i) conservative non-invasive strategy (invasive coronary angiography is not planned), (ii) invasive coronary angiography is planned but has not yet occurred, (iii) an invasive coronary angiogram has been performed and the patient has been referred or undergone CABG surgery, (iv) an invasive coronary angiogram has been performed and the patient has had at least one drug eluting stent implanted, (v) an invasive coronary angiogram has been performed and the patient has had only bare metal stents implanted (this group will also include patients who have had balloon angioplasty only performed without stent implantation), (vi) an invasive coronary angiogram has been performed and the patient is to receive medical management only.

Block size will be randomly determined, and each block will contain both treatments in a 1:1 ratio.

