4.6 Secondary outcomes

The interpretation of trial findings for secondary outcomes will focus on the effect size and 95% CI. No formal adjustment will be made to significance levels to allow for multiplicity.

For each of the following secondary outcomes (appendix C), events are defined as the time to first outcome event during follow-up from date of the index myocardial infarction. Follow-up will be censored at competing causes of death or 15 months from date of MI, whichever occurs first.

Efficacy

- Cardiovascular death and non-fatal myocardial infarction
- Cardiovascular mortality (cardiac and non-cardiac)
- Myocardial infarction (fatal and non-fatal)
- Stent thrombosis
- Coronary revascularisation
- Thrombotic stroke

Safety

- Non-cardiovascular death (including fatal bleeding) and major non-fatal bleeding
- Non-cardiovascular death (including fatal bleeding)
- Major fatal and non-fatal bleeding
- Hospitalisation for bleeding
- Intracranial haemorrhage
- Gastrointestinal bleeding

The analysis will follow that specified for the primary outcome in section 4.5. The number and proportions of participants with an event for individual components of the secondary outcomes will also be reported alongside the composite.

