4.9 Extended follow-up

The analyses of the primary and secondary outcomes will be repeated censoring at the date of last available follow-up.

⁴ The Haemoglobin outcome in the protocol will not be analysed, as the data is not nationally linked.

5. Validation and QC

The following will be done by a second statistician:

1. The code will be checked and run to ensure results are as stated
2. Check of data fidelity from raw data to SAS data files (random selection)
3. Check treatment allocation consistent between UK and NZ datasets
4. Check of ICD10/OPCS4 (or equivalents codes) in SMR01 (or equivalent datasets) map to the study SAP
5. The statistical report will be read and sense-checked.

6. Data sharing

Data will be stored inside a Trusted Research Environment (TRE) managed by AIMES on behalf of ECTU for 12 years. Access to the data needs to be approved, there are no data sharing agreements, protocols or contracts in place or planned.

7. References

1. Royston, P. and M.K. Parmar, *The use of restricted mean survival time to estimate the treatment effect in randomized clinical trials when the proportional hazards assumption is in doubt*. Stat Med, 2011. **30**(19): p. 2409-21.
2. Burke, D.L., J. Ensor, and R.D. Riley, *Meta-analysis using individual participant data: one-stage and two-stage approaches, and why they may differ*. Statistics in Medicine, 2017. **36**(5): p. 855-875.
<https://doi.org/10.2307/2670170>

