Appendix C

Outcomes defined used the following codes and positions specified below following the date of index MI unless otherwise specified. If the code is not identified in any admissions/deaths then they will be assumed to not have the outcome of interest.

Data sources

Scotland: SMR00 / SMR01 / NRS Deaths / Prescribing Information System / Scottish Blood Transfusion Database

England: Hospital Episode Statistics / Civil Registrations of Death / Medicines dispensed in Primary Care (NHSBSA data)

Outcome	Code (ICD-10 , OPCS4)
All-cause mortality	Any record of death.
Non-cardiovascular death (including fatal bleeding) and major non-fatal bleeding	
Death due to a non-cardiovascular cause
 
Primary position for cause of death
 
Ax, Bx, Cx, Dx Ex, Fx , Gx , Hx , Jx, Kx , Lx , Mx , Nx , Ox , Px , Qx , Rx , Sx , Tx , Ux , Vx , Xx , Yx , Zx.
 
OR
 
Hospitalisation for bleeding
 
Primary or first secondary position
 
I60x, I61x, I62x, S06.4x, S06.5x, S06.6x, K92.0x, K92.1x, K 92.2x, I85.0x, I98.3x, K22.6x, K25.0x, K25.2x, K25.4x, K25.6x, K26.0x, K26.2x, K26.4x, K26.6x, K27.0x, K27.2x, K27.4x, K27.6x, K28.0x, K28.2x, K28.4x, K28.6x, K29.0x, K62.5x, K66.1x, R58x, I23.0x, I31.2x, I69.0x, I69.1x, I69.2x, H21x, H35.6x, H31.3x, H43.1x, H44.8x, H45.0x, R04.0x, R04.1x, R04.2x, R04.8x, R04.9x, T81.0x, D62x, N83.7x, N93.8x , N93.9x, O03.1x, O03.6x, O04.1x, O04.6x, O05.1x, O05.6x, O06.1x, O06.6x, O20.8x, O20.9x, O46x , O67x, O07.1x, O07.6x, O08.1x, O71.7x , O72.0x , O72.1x , O72.2x , O90.2x , P26.1x , R31x , M25.0x.
 
OR

	
Primary procedure position (OPSC4)
 
E05x , E058x , E059x , F162x , D041x , E203x , F365x , G523x , H212x , H531x , K681x , P093x , P271x , T301x , Y221x , T032x , Y221x , T032x , Y321x , V032x , A052x , A053x , A054x , A103x , A401x , A411x

Non-cardiovascular death (including fatal bleeding)	
Primary cause of death
 
Ax , Bx , Cx , Dx , Ex , Fx , Gx , Hx , Jx , Kx , Lx , Mx , Nx , Ox , Px , Qx , Rx , Sx , Tx , Ux , Vx , Xx , Yx , Zx

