Myocardial infarction (fatal and non- fatal)	
Myocardial infarction after the Index Admission Discharge Date
 
Primary or first secondary position
 
I21x, I22x
 
OR
 
Death due to myocardial infarction
 
Primary cause of death
 
I21x, I22x

Stent thrombosis	
Stent thrombosis
 
Primary or first secondary position
 
T82.8x

Coronary revascularisation	
Coronary revascularisation after the Index Admission Discharge Date
 
Primary procedure position (OPCS4)

	K40x, K41x, K42x, K43x, K44x, K45x, K46x, K47x, K48x, K49x, K50x, K75x.
Thrombotic stroke	
Ischaemic stroke
 
Primary or first secondary position
 
I63x
 
OR
 
Death due to ischaemic stroke
 
Primary cause of death
 
I63x

Blood transfusion	Any record of transfusion
Iron therapy	
Prescribed Iron Therapy
 
Approved drug names: FERROUS SULPHATE, FERROUS FUMARATE, FERROUS GLUCONATE, FERRIC MALTOL, FERROUS CALCIUM CITRATE, FERROUS GLYCINE SULFATE, IRON CARBOXYMALTOSE, SODIUM FEREDETATE, IRON CARBOXYMALTOSE, IRON DEXTRAN, IRON SUCROSE, VENOFER, FERINJECT

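### The myocardial infarction outcome has no reliable test for telling a new infarction from the index one, and its fatal and non-fatal limbs start on different dates

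*SAP*

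**What the plan says.** SAP Appendix C builds the outcome of fatal and non-fatal myocardial infarction from two limbs.

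- **Non-fatal limb.** I21x or I22x in the "Primary or first secondary" position, restricted to "Myocardial infarction after the Index Admission Discharge Date". The composite of cardiovascular death and non-fatal infarction uses the same rule.
- **Fatal limb.** "Death due to myocardial infarction", meaning I21x or I22x as primary cause of death. The row gives no start date of its own, so the Appendix C header applies: "Outcomes defined used the following codes and positions specified below following the date of index MI unless otherwise specified".

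SAP 4.6 sets the clock for both limbs: "events are defined as the time to first outcome event during follow-up from date of the index myocardial infarction". It also sets the end: "Follow-up will be censored at competing causes of death or 15 months from date of MI, whichever occurs first". SAP 4.9 then adds a longer version: "The analyses of the primary and secondary outcomes will be repeated censoring at the date of last available follow-up".

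The SAP does not say whether the index discharge ends an episode, one hospital's stay, or a continuous stay including transfers. It specifies no minimum interval from the index event and no adjudication of infarctions.

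**The concern.** Protocol 4.2 admits only patients with a recent type 1 infarction, so every participant's hospital record can already contain the codes that define the outcome. A single undefined date on one limb has to separate the old infarct from a new one.

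The design makes early onward care likely. Protocol 5.5.1 has a stratum described as "ii) invasive coronary angiography is planned but has not yet occurred", and another that includes patients referred for bypass surgery.

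Protocol 11.6 names the risk that 3 months of therapy is too brief and leads to excess atherothrombotic events. Infarction, and cardiovascular death or infarction, are the secondary outcomes that speak most directly to that risk. If index-infarct records are mixed into them, the comparison is partly made on events that treatment duration could not have changed.

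**Working it through.** **1. The two limbs side by side**

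| | Non-fatal limb | Fatal limb |
|---|---|---|
| Codes | I21x, I22x | I21x, I22x |
| Position | primary or first secondary | primary cause of death |
| Start | after index discharge (undefined) | after index infarction date |
| End | 15 months, or competing death | 15 months |
| New-admission or new-event test | none | none |
| Outcomes affected | MI; CV death/MI composite | MI only |

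The fatal limb cannot alter the composite, because any I-coded death already counts there as cardiovascular death.

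**2. Three patients under the rule as written**

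- *Transfer.* A patient awaiting angiography leaves the first hospital for another centre, and the second record carries I21. If the index discharge means leaving the first hospital, this counts. If it means the end of the continuous stay, it does not.
- *Planned return.* A patient referred for bypass surgery is discharged and readmitted for the operation, with I21 in first secondary position for the index infarct. This counts on either reading.
- *Death before discharge.* A patient randomised on the ward dies of the index infarct. This counts as a fatal MI, although a non-fatal event on the same day could not.

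The first two cases assume that coders carry I21/I22 forward for the index infarct. The documents are silent on this.

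**3. Would another step in the plan catch it?**

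- The SAP section 5 quality check on codes compares them with the SAP, so it would confirm the rule as written.
- The SAP 4.6.1 analysis of code position covers safety outcomes only.
- The SAP 4.5.2 landmark analysis selects patients alive at 3 months. It does not select patients free of a recorded infarction.
- Protocol 7.1 allows access to clinical records when needed, but no step uses them to check infarctions.

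**4. Direction**

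SAP 4.5.2 notes that the arms are treated alike until month 3. Early false events should therefore fall about equally in both arms and pull a ratio towards 1. Because the analysis is time to first event, a false early event also hides a true later one.

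**5. Illustrations (all rates assumed)**

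No figure in the documents rests on the MI outcome, so there is nothing to reproduce.

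*First illustration.* Take 4,576 / 2 = 2,288 per arm. Assume a true risk of 2% to month 3 in both arms, then 4% (3-month arm) against 3% (12-month arm). Let f be the share of patients whose index infarct is re-counted early.

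Risk per arm = 2% + f + (1 − f) × 4% or 3%; z = difference / √[(p₁(1 − p₁) + p₂(1 − p₂)) / 2,288].

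| f | 3-month arm | 12-month arm | Risk ratio | Difference (points) | z |
|---|---|---|---|---|---|
| 0 | 6.00% | 5.00% | 1.20 | 1.00 | 1.48 |
| 1% | 6.96% | 5.97% | 1.17 | 0.99 | 1.36 |
| 3% | 8.88% | 7.91% | 1.12 | 0.97 | 1.18 |
| 5% | 10.80% | 9.85% | 1.10 | 0.95 | 1.06 |

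*Second illustration.* Assume 200 true events and a true hazard ratio of 1.5, so 120 against 80 events. Split the false events equally and approximate the hazard ratio by the ratio of counts.

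- If 5% of recorded events are false: 200 / 0.95 = 210.5 recorded, 5.26 false per arm, ratio 125.26 / 85.26 = 1.47.
- If 30% are false: 200 / 0.70 = 285.7 recorded, 42.86 false per arm, ratio 162.86 / 122.86 = 1.33.
- Power by the Schoenfeld formula (two-sided 5%) falls from 82% to 80% and 66% respectively.

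**The case against.** The strongest reply is that the plan already has sensible limits, and that a reader might infer more than the documents support.

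- *That every I21/I22 record counts.* It does not; only the first two diagnostic positions do.
- *That infarction deaths have no date limit.* They do: after the index infarction and, in the main analysis, within 15 months. What is missing is a post-discharge limit.
- *That transfers are scored as new infarctions.* This depends on an undefined date. If it ends the continuous stay, they are already excluded.
- *That the rule tilts the result towards shorter therapy.* It does not. The false events are expected in both arms, so the ratio is diluted whichever way the true effect runs.

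Each of these stands as a limit on the claim. It is also fair that the outcome is labelled fatal and non-fatal infarction, not recurrent infarction, so a certified index-infarct death fits the label. That does not explain why the two limbs should start on different dates.

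The illustrations rest on invented rates. In the first, z is only 1.48 with no misclassification, so no significance conclusion changes. The absolute difference, which SAP 4.5 also asks for and 4.6 carries over to secondary outcomes, barely moves. SAP 4.6 puts the emphasis on effect sizes and intervals, and the protocol chose all-cause mortality to capture the trade-off. This keeps the point at the level of secondary outcomes but does not remove it: the hazard ratio is one of those effect sizes.

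**Conclusion.** The concern holds in limited form. As written, Appendix C can score as MI outcomes the onward leg of a transfer (if the date means the first hospital's discharge), a planned early return coded I21/I22, and a death from the index infarct before discharge. The non-fatal rule affects both infarction and the cardiovascular death/MI composite. The fatal rule affects infarction only. All-cause mortality is not affected.

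The expected consequence is a relative effect diluted towards 1. It rests on two assumptions: coders retain I21/I22 for the index infarct on later records, and such records fall about equally by arm. The documents give no infarction, transfer or re-coding rates, so the number of misclassified events cannot be calculated. The figures above show direction and scale under stated assumptions and are not estimates for this trial.

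The definition should be tightened before analysis. Clarifying the date alone would settle transfers but would leave planned returns and the mismatch between the limbs.

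**What to change.** In the infarction and cardiovascular death/MI rows of Appendix C:

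1. Define the index discharge as the end of the continuous hospital stay, including transfers, and apply it in the same way in Scotland, England and New Zealand. Appendix C currently names sources for the first two only, although SAP 4.1 includes New Zealand.
2. Count a non-fatal infarction only in a new non-elective, non-transfer admission that starts after that stay.
3. Give the fatal limb of the MI outcome the same start date. Deaths in the index stay would still count as all-cause and, where so coded, cardiovascular death, but not as a new infarction.

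Report three sensitivity analyses: the current definition; primary position only; and a prespecified minimum interval from the index infarction. The last is needed because an early emergency readmission still coded to the index infarct would pass rule 2. The documents give no interval, so the trial team must set one before seeing results by arm.

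The cost is Appendix C wording and some programming on linked records. The main definition would miss a genuine infarction during an elective stay and a genuine fatal reinfarction during the index stay; the current definition, kept as a sensitivity analysis, retains both. Whether admission-type and transfer fields are available must be confirmed in each country's data, because the documents do not show it.

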1.3 REDUCING ATHEROTHROMBOTIC EVENTS

In patients with acute coronary syndrome, the risk of a recurrent adverse cardiac event is related to the burden of coronary artery disease. Coronary intervention by either percutaneous coronary intervention or coronary artery bypass graft surgery effectively reduces this risk by relief of obstructive coronary disease. Coronary artery bypass graft surgery generally provides complete revascularization because

the bypass grafts are placed in distal locations ‘bypassing’ the more proximal disease. By contrast, percutaneous coronary intervention provides a focal treatment to individual lesions, and treatment may be incomplete because not all of the lesions may be treated by stents. Audit of the British Cardiovascular Society Intervention (BCIS) database indicates that in 2013 to 2014, 49% of all percutaneous coronary intervention procedures were associated with residual disease (≥ 1 stenosis $>50\%$ severity), fulfilling the criteria for incomplete revascularisation. Patients with acute coronary syndrome and incomplete revascularisation have a residual burden of coronary disease that is a substrate for recurrent plaque rupture, coronary thrombosis and future cardiac events. Prolonged dual antiplatelet therapy may mitigate this risk and prolonged therapy may benefit those patients with incomplete revascularisation following the index procedure to a greater extent than patients with complete revascularisation.

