4.2 INCLUSION CRITERIA

For inclusion in the study, participants will fulfil the following criteria:

- Aged ≥ 18 years
- Clinical diagnosis of type 1 myocardial infarction within 12 weeks
- In the opinion of the attending clinician requires dual anti-platelet therapy with aspirin and a P2Y12 receptor antagonist.
- Resident in the country of recruitment with their unique health identifier
- The attending clinician has equipoise regarding the duration of therapy
- Provision of informed consent

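### The coronary revascularisation outcome counts a CABG for which the patient was already referred at randomisation, if it is done after index discharge; this dilutes one secondary efficacy outcome towards no difference.

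*SAP*

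**What the plan says.** SAP Appendix C sets a general rule, "Outcomes defined used the following codes and positions specified below following the date of index MI unless otherwise specified", and then gives coronary revascularisation a later start: "Coronary revascularisation after the Index Admission Discharge Date". The qualifying codes, in the primary procedure position, are "K40x, K41x, K42x, K43x, K44x, K45x, K46x, K47x, K48x, K49x, K50x, K75x". SAP 4.6 lists the outcome under efficacy and analyses it as time to first event from the index MI, with censoring at competing death or 15 months.

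Protocol 5.5.1 defines stratum (iii) as "an invasive coronary angiogram has been performed and the patient has been referred or undergone CABG surgery" and stratum (ii) as "invasive coronary angiography is planned but has not yet occurred". Protocol 4.2 admits patients with "Clinical diagnosis of type 1 myocardial infarction within 12 weeks", and SAP 4.5.4 says the single study contact may take place in a ward or at an out-patient facility.

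Neither document limits the outcome to unplanned, urgent or ischaemia-driven procedures, and there is no blanking period after discharge. The sensitivity analyses in SAP 4.6.1 cover the competing risk of death and, for safety outcomes only, diagnostic position.

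**The concern.** Starting the outcome at index discharge keeps treatment of the index event out of the count, provided that treatment is finished before the patient goes home. For a stratum (iii) patient who is discharged to await surgery, it is not. The operation was decided before allocation, yet it is scored as an efficacy event.

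Two things follow. First, events that do not reflect the duration of therapy are added to both arms, which pulls the estimated ratio towards 1. Secondly, the patient's first event is used up, so a later procedure that might reflect treatment is never counted. A ratio close to 1 could then be read as reassurance about ischaemic procedures when part of it comes from work already booked.

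**Working it through.** **Figures in the plan.** The plan gives no rate, effect size or power for revascularisation, so there is nothing of its own to reproduce for this outcome. Its sample size concerns mortality only: 16.9% against 0.9 × 16.9% = 15.21%, 85% power, two-sided 5%, no continuity correction. This gives 8,472 per group, as stated in protocol 9.2, and does not depend on this point.

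**Does a planned CABG get through the definition?**
1. Stratum (iii) covers both groups: "the patient has been referred or undergone CABG surgery". Patients who are only referred still have the operation to come.
2. Enrolment can be up to 12 weeks after the MI and may be at an out-patient facility, so some patients may already be at home when randomised.
3. The CABG codes are on the outcome list, and the only filter is the discharge date. A CABG during the index stay is excluded; one after discharge counts.
4. Follow-up runs from the MI, so a CABG done after discharge but before a late randomisation would count too.
5. Appendix C does not say which date is the index discharge after an inter-hospital transfer. If it is the date of leaving the first hospital, an operation at the receiving hospital also counts.
6. Adjusting for cardiac history does not remove these events. The landmark analysis in SAP 4.5.2 selects on survival to 3 months, not on freedom from a planned procedure.

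**Upper bound from the documents.** Protocol 9.1 expects just under 7.5% of patients to have CABG or bare-metal PCI: 0.075 × 4,576 = 343 UK patients at most. The share referred for CABG, discharged and operated on later is not given and must be smaller.

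**Dilution (assumed rates).** Let planned post-discharge procedures occur in a share q of each arm, unplanned ones in a share u of the 12-month arm, and let R be the true ratio for unplanned procedures. Then observed ratio = (q + uR)/(q + u).

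| q | u | planned share of 12-month-arm events | R = 1.25 | R = 0.80 |
|---|---|---|---|---|
| 1% | 8% | 1/9 = 11% | (1 + 10)/9 = 1.222 | (1 + 6.4)/9 = 0.822 |
| 3% | 5% | 3/8 = 37.5% | (3 + 6.25)/8 = 1.156 | (3 + 4)/8 = 0.875 |

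The range for q is meant for planned procedures of any kind. If referred CABG alone is below 1%, the dilution is smaller than in the first row.

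**Against sampling error.** Take 2,288 UK patients per arm and the second row with R = 1.25.
- Unplanned only, 5% against 6.25% (114.4 and 143 events): SE of the log ratio = √(1/114.4 + 1/143 − 2/2,288) = 0.122, and z = 0.223/0.122 = 1.83.
- All procedures, 8% against 9.25% (183.0 and 211.6 events): SE = √(1/183.0 + 1/211.6 − 2/2,288) = 0.0965, and z = 0.145/0.0965 = 1.50. The ratio is 1.16 with 95% CI 0.96 to 1.40.

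**Power.** With u = 5% and a hazard ratio of 1.25, the comparison risk is 1 − 0.95^1.25 = 6.21%. Each arm's risk becomes q + (1 − q) × risk. At 2,288 per arm, power is 43% with q = 0, 37% with q = 1% and 31% with q = 2.5%.

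**Later procedures lost.** If planned and unplanned procedures are independent, between 1% × 5% = 0.05% and 3% × 8% = 0.24% of 4,576 patients are affected, or about 2 to 11.

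**The case against.** The strongest reply is that the SAP carries out the protocol faithfully. Protocol 7.1 and Table 3 name coronary revascularisation, meaning PCI and CABG, without any restriction to unplanned procedures. This is one of twelve secondary outcomes, SAP 4.6 reads them on effect size and interval, and the UK data have limited power for it even when planned procedures are removed. In the worst illustrated case the diluted interval still contains the true 1.25; in the mildest, the shift is (0.223 − 0.201)/0.089 = 0.25 standard errors. All of this stands. It limits the weight of the point but does not make a pre-booked operation informative about duration of therapy.

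A reader might go further in four ways that the documents do not support.
- **Stratum (ii) procedures were also fixed in advance.** Only the angiogram was planned. Whether a procedure follows is not known at randomisation, Appendix A allows for patients who have none, and in an open-label trial the later decision could depend on allocation.
- **Staged PCI is shown to be common.** Protocol 1.3 reports that "49% of all percutaneous coronary intervention procedures were associated with residual disease", but this is an audit of residual disease across all PCI. It does not measure staged or post-discharge procedures.
- **Only emergency admissions should count in the other strata.** Neither document says that admission type is available, and such a rule would drop genuine elective revascularisation for recurrent symptoms.
- **The result is biased towards one arm.** Referral precedes randomisation, so the number referred should balance. An effect of open-label allocation on the timing of surgery cannot be excluded, but nothing in the documents shows one.

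**Conclusion.** The point holds for stratum (iii). As written, Appendix C scores a CABG already referred for at randomisation as an efficacy event whenever it follows index discharge, and nothing elsewhere in the plan removes it. The consequence is a modest dilution of one secondary outcome and some loss of power. It would blur a real difference rather than hide it. The illustrated size, 1.25 seen as about 1.22 to 1.16 and 0.80 as about 0.82 to 0.88, rests on assumed rates (planned 1-3%, unplanned 5-8%, planned procedures equal in both arms), none of which the documents give. The mortality analysis is not affected.

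Stratum (ii) is weaker ground. There is still an awkward overlap: Appendix A uses procedures after the MI to assign these patients to a cardiac history group, so one procedure can both define the group and count as an outcome. That justifies a sensitivity analysis, not a new main definition.

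**What to change.** In SAP Appendix C, under coronary revascularisation:
1. For patients randomised in stratum (iii), do not count the first CABG after the index MI; count any later procedure. Where that CABG was done during the index stay, the rule changes nothing.
2. State that inter-hospital transfers belong to the index admission, so that the index discharge date is the end of the whole episode.
3. Report the current all-procedure definition alongside.
4. Add a sensitivity analysis that does not count the first procedure after the MI in stratum (ii). Leave the main definition for that stratum, and for the others, as it is.

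The rule for stratum (iii) needs only the randomisation stratum and the procedure codes already held. The cost is a few lines of SAP text, modest programming and slightly fewer counted events. An occasional unplanned first CABG in stratum (iii) will be left out; the all-procedure result reported alongside shows how much that matters. Because the protocol names the endpoint without restriction, the SAP should record the change and the reason for it.
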